5.0 Treatment Plan

Table 1- Protocol stages

| | Day of Surgery- Pre-op | Intraoperative | 15 departure from PACU | 6 hours postop | 12 hours postop | 24 hours postop | 36 hours postop | 48 hours postop |
|------------------------------------------------------------------------------------|---------------------------|----------------|---------------------------------|----------------------|-----------------------|-----------------------|-----------------------|-----------------------|
| Pre-operative pain score | X | | | | | | | |
| Preoperative multimodal regimen unless contraindicated | X | | | | | | | |
| Receive ISB with Exparel or plain bupivacaine + adjuvants | X | | | | | | | |
| Receive short-acting IV opioids if needed | | X | | | | | | |
| Rescue opioids if needed | | | X | X | X | X | X | X |
| Postoperative multimodal regimen | | | | X | X | X | X | X |
| Pain score assessment in diary | | | X | X | X | X | X | X |
| Patent diary of narcotic use | | | X | X | X | X | X | X |
| Study coordinator contact via phone call | | | | | | X | | X |
| Patient satisfaction assessed via Likert scale. Review of potential adverse events | | | | | | | | X |

5.1 Study-Related Activities

Patients will be recruited from 2 sites- Wake Forest Baptist Health (Main Campus) and WFBH Davie. Patient involvement in the study will be initiated upon scheduling of their surgery with the Anesthesiology team. Eligible subjects will be identified via eligibility checklist (Appendix A) and contacted via phone call to inform them of the study and give them a brief overview. On the day of surgery, the consent for the study will be obtained after a pre-operative assessment and prior to initiating the regional block by the RAAPM team.

Single Injection interscalene brachial plexus nerve block with adjuvants vs. Liposomal bupivacaine interscalene brachial plexus nerve block for total shoulder arthroplasty

[figure not shown]
The study coordinator will then assign the patients will receive a study number, and the patient will be randomized by computer software algorithm to one of the study arms:

1. ISB using liposomal bupivacaine
2. ISB using plain bupivacaine with adjuvants

The study will be double blinded to patients, the perioperative nurses, the surgeon, and the study coordinators contacting the patient post-surgery.

To monitor our primary outcomes, patients will be asked to rate their pain level on a visual analog scale (Table 2, Appendix D) upon discharge from the PACU. Following discharge, they will continue to get every 12-hour pain assessments performed by research staff in person and/or over the phone (if they are discharged) until 48 hours have passed.

Table 2: Visual Analog Scale

Additionally, upon discharge, patients will be given a sheet to record the amount of narcotics and the time that they were used (Appendix G). At the 48-hour mark, patient's will be asked to rate their satisfaction with the procedure, and their willingness to recommend it, via Likert scale (Appendix E).

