6.1 Analysis of Primary Objective

6.1.1 The VAS-NRS scale is an 11-point scale that assesses pain from 0- “No pain” to 10- “Worst possible pain”. For this study, a difference of ≥ 2 points will be considered to be clinically significant. Pain scores will be taken measured on departure from the PACU and at each 12-hour interval, and average pain scores for each cohort will be calculated. The area under the curve (AUC) for each cohort will be calculated using the least squares method. The inferiority threshold will be set as ≥ 2 points over 48 hours, which would result in an AUC difference of 96 point-hours.

Prior studies have found an AUC48 for ISB using liposomal bupivacaine to be 136.4 with a standard error of 12.09.¹⁰ There are no data evaluating the AUC48 for ISB using plain bupivacaine with adjuvants; however we estimate that the

Single Injection interscalene brachial plexus nerve block with adjuvants vs. Liposomal bupivacaine interscalene brachial plexus nerve block for total shoulder arthroplasty

pain scores will be within 20% of that of liposomal bupivacaine, resulting in an AUC48 of 163.0 or below, and a similar standard error of 12.09.

With a 2-sample t test using $\alpha = 0.05$ and $\beta = 0.1$, the study will be powered to detect a difference of 96 point-hours between the 2 groups with 36 subjects per arm.

To test for differences in these AUC between the 2 arms, an independent t-test will be used; if the observed p-value is <0.05 , statistical significance will be assumed. Two-sided t-test will be performed for statistical analysis once data collection is complete.

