6.3 Power and Sample Size

We will have a power of 80%, as described in 10.1.1, with a sample size of 36 patients in each arm for a total of 72 patients, plus 8 patients to allow for attrition, for a total of 80 patients.

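### Two sites recruit, but no use of site is described in the randomisation, the primary t-test or the forms; stratifying and adjusting for site would be a cheap, small gain in precision

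*Combined protocol and SAP*

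**What the plan says.** Section 5.1 (Study-Related Activities) states "Patients will be recruited from 2 sites": a main campus and a second hospital of the same health system. On allocation it says that "the patient will be randomized by computer software algorithm to one of the study arms". It does not give the type of algorithm, block sizes or stratification factors.

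Section 6.1 gives the primary analysis: "To test for differences in these AUC between the 2 arms, an independent t-test will be used". It adds that "Two-sided t-test will be performed for statistical analysis once data collection is complete". No covariate is named, and sections 6.1 to 6.3 do not mention site. Section 6.3 plans the trial "with a sample size of 36 patients in each arm for a total of 72 patients", plus 8 for attrition.

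Appendix B and Appendix H list the data to be recorded. Neither has a field for site.

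Two passages bear on how far the sites could differ. Section 5.1 has the regional anaesthesia team involved at consent and block, and has pain scored in person or, after discharge, by phone. Section 5.3 applies common anaesthetic criteria to every patient.

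**The concern.** The outcome is self-reported pain over 48 hours, with as-needed analgesia. Two hospitals may differ in block operators, discharge timing, and so in the share of scores taken by phone. The documents do not say that they do. If they do, an analysis that ignores site carries the difference as noise. Unless allocation is stratified, the arms can also differ by chance in their mix of sites.

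What is at stake is precision. The stated purpose in section 1.0 is non-inferiority, and section 6.1 sets a threshold of 96 point-hours. The width of the interval around the AUC difference therefore matters, and a site term can narrow it without enrolling anyone. Without a site field on the forms, the adjustment would also have to be reconstructed from other records.

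**Working it through.** **Inputs from the documents**
- AUC48 in the liposomal arm of the cited trial: 136.4, SE 12.09 (6.1). No SD or n is given for the AUC.
- 48-hour score in the same source: SD 2.88, SE 0.36 (6.2.1).
- Expected AUC48 in the comparator: 163.0, a difference of 26.6 (6.1).
- Threshold: 2 points × 48 h = 96 point-hours (6.1).
- 36 per arm, 72 in total (6.1, 6.3).

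**Assumptions (not in the documents)**
- AUC SD: n = (2.88/0.36)² = 64, so SD = 12.09 × √64 = 96.7. This takes the AUC to rest on the same 64 patients.
- Share of patients at the smaller site, p: 25% to 50%.
- Site gap, g: 0.5 to 1 point of mean pain over 48 h, that is 24 to 48 point-hours.

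**The plan's own sample size**

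For a two-sided test with α = 0.05, 90% power and a difference of 96: n = 2 × (1.960 + 1.282)² × 96.7² / 96² = 21.3, so 22 per arm. With 80% power it is 15.9, so 16. A figure of 36 per arm would need an SD of about 126 (90% power) or 145 (80% power), and neither is stated. Because the AUC SD is not given, 36 is neither confirmed nor refuted. Both larger SDs are carried below as a sensitivity check.

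**Share of variance due to site**

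R² = p(1 − p)g² / SD². Equivalent patients = 72 × (1/(1 − R²) − 1). Narrowing of the interval = 1 − √(1 − R²).

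| p | g (point-hours) | R² | Patients in 72 | Interval narrower by |
|---|---|---|---|---|
| 25% | 24 | 1.2% | 0.8 | 0.6% |
| 50% | 24 | 1.5% | 1.1 | 0.8% |
| 25% | 48 | 4.6% | 3.5 | 2.3% |
| 50% | 48 | 6.2% | 4.7 | 3.1% |

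If the SD were 126 or 145, the 1-point rows would fall to 2% to 4% of variance, or about 1.5 to 3 patients.

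**Power at 36 per arm**

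Here 96.7 is taken as the SD within site, so leaving site out raises the SD to √(96.7² + p(1 − p)g²), at most 99.7.
- Detecting a difference of 96, two-sided 0.05: 98.8% with site removed from the error; 98.3% to 98.7% without.
- Non-inferiority (margin 96, true difference 26.6, one-sided 0.025): 86.1% with site removed; 84.0% to 85.7% without. The largest loss is 86.1 − 84.0 = 2.1 percentage points.

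**Cost of the extra term**

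The critical t value moves from 1.9944 (70 df) to 1.9949 (69 df), which is negligible. If allocation is not stratified, arm and site are slightly correlated by chance. In simulation with no site gap, the SD of the estimated difference rose from 22.57 to 22.72, or 0.7%. That roughly cancels the gain at a 0.5-point gap. Stratified allocation avoids this loss.

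**Validity of the t-test**

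Simulations used p = 30% and 50%, with 20,000 runs per setting for type I error.
- Unstratified allocation with the unadjusted t-test: type I error 0.049 to 0.051 for site gaps of 24 to 96 point-hours, so valid.
- Stratified allocation with the unadjusted t-test: 0.042 to 0.046 at a gap of 48 and about 0.03 at 96, so conservative. With the site term added, it returned to about 0.05.

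**The case against.** The strongest reply is that nothing here is wrong, only unstated, and that the sites may be much alike. They share one health system, the regional anaesthesia team is involved, anaesthetic criteria are common to all patients, and phone scoring follows discharge status rather than hospital. All of that stands. Site is a possible source of variation here, not a documented one, and the gain could be nil.

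A reader might infer four stronger things that the documents do not support.
- **That randomisation ignores site, or leaves the arm sizes to chance.** Section 5.1 is silent on the algorithm, and a figure there could not be seen in the available text. Blocking or stratification is neither described nor ruled out. Unequal arms would matter little in any case: a 35:45 split of 80 has the precision of 2 × 35 × 45 / 80 = 39.4 per arm, above the planned 36 before attrition.
- **That the primary comparison is biased or invalid.** Under unstratified allocation the t-test keeps its type I error.
- **That chance imbalance in site mix is a further cost on top of the lost precision.** It is the same cost, because the standard error of the t-test already allows for it.
- **That a site term would deliver the non-inferiority conclusion.** Section 6.1 specifies a two-sided test of difference and no confidence interval. That mismatch is separate, and adjusting for site does not repair it.

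**Conclusion.** The point holds as a low-cost improvement. Two sites are named, no use of site is described in allocation or in the primary analysis, and the forms do not record site. The size rests on the derived SD of 96.7 and on assumed site gaps and shares. Under them the gain is slight at a 0.5-point gap. At 1 point the interval narrows by 2% to 3%, and the power gain is at most about 2 percentage points. The larger SDs that would reproduce 36 per arm make the share of variance smaller still. No conclusion of the trial is put at risk if the plan is left as it is.

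**What to change.** - **Section 5.1:** state that allocation uses concealed permuted blocks of varying size, stratified by site. If enrolment has started, keep the existing list, describe it, and make only the analysis and form changes.
- **Section 6.1:** estimate the arm difference in AUC and its confidence interval from a linear model with arm and site, specified before unblinding.
- **Sections 6.2.1 and 6.2.2:** use the same model for the 48-hour score and for opioid use. Opioid use would be on the log scale that the geometric mean already implies, with a stated rule for patients who use none.
- **Section 6.2.3:** leave as it is. A linear model is not an obvious replacement for Fisher's exact test on the Likert and binary items.
- **Appendix H:** add a site field.

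The first two changes belong together: if allocation is stratified, the site term should be in the model, because the unadjusted t-test would then be conservative.

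The cost is a randomisation setting, one form field, a few lines in section 6, and one degree of freedom out of 70. If the sites do not differ, nothing is gained.

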5.2 Treatment Administration

Patients assigned to the ISB with liposomal bupivacaine group will receive a 20cc solution of 133mg liposomal bupivacaine (10mL expanded with 10mL 0.25% plain bupivacaine) in an interscalene block, conducted via Ultrasound guidance.

Patients assigned to the ISB with plain bupivacaine and adjuvants group will receive a 20cc solution of plain bupivacaine 0.25% with adjuvants (clonidine 1.6mcg/mL, epinephrine

Single Injection interscalene brachial plexus nerve block with adjuvants vs. Liposomal bupivacaine interscalene brachial plexus nerve block for total shoulder arthroplasty

2.5mcg/mL, dexamethasone 0.1mg/mL, and buprenorphine 150mcg) in an interscalene block, conducted via Ultrasound guidance.

The absolute dosages of medications will be as follows: either 133mg liposomal bupivacaine with 25mg plain bupivacaine OR 50mg plain bupivacaine with adjunct medicines: 32mcg clonidine, 50mcg epinephrine, 2mg dexamethasone and 150mcg buprenorphine.

The treatment will be administered by either an attending anesthesiologist, or a resident anesthesiologist under the supervision of an attending.

5.3 General Concomitant Medication and Supportive Care Guidelines

This local anesthetic will get delivered at the time of surgery by an attending or resident anesthesiologist. Standardized anesthetic criteria will be applied to all patients enrolled in the study. Pre-operatively, all patients will receive multi-modal therapy, such as acetaminophen 1000 mg PO, celecoxib 200 mg PO, and gabapentin 300 mg PO or pregabalin 150 mg PO unless contraindicated based on past medical history.

Intraoperatively, patients will only receive short acting opioids for analgesia, such as fentanyl as needed. Intraoperative ketamine and dexamethasone will be avoided. Postoperative non-opioid medications will supplement as needed opioid mediations for analgesic management. Postoperative pain management for breakthrough pain will include the following options: IV fentanyl, IV hydromorphone, or PO oxycodone.

Patients will receive full supportive care as medically necessary, including transfusions of blood and blood products, antibiotics, antiemetics, etc. Medications considered necessary for the patient's well-being may be given as long as they are considered safe in the postoperative period and clinically indicated. The reason(s) for treatment, dosage, and dates of treatment will be recorded on the flow sheets.

Anesthesia monitoring for the study procedure will follow institutional guidelines. It includes the following: vital signs (blood pressure, heart rate, respiratory rate, and oxygen saturation) will be initiated in the regional anesthesia holding room at the time of procedure time out, and includes parameters measured every 5 minutes until subject goes to the operating room. At that time routine anesthesia monitoring continues with vital signs every 3 minutes. Once the subject enters the post anesthesia care unit the vital sign monitoring is every 15 minutes until discharge.

5.4 Duration of Follow Up

Single Injection interscalene brachial plexus nerve block with adjuvants vs. Liposomal bupivacaine interscalene brachial plexus nerve block for total shoulder arthroplasty

Patients will be followed by research personnel upon arrival to the PACU, again 6 hours postoperatively, and then at 12, 24, 36 and 48 hours after surgery both in the hospital and at home via phone call.

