1.0 Introduction and Background

In 2011, liposomal bupivacaine received FDA approval for the use of local surgical site infiltration, and its use has become common for a variety of abdominal, gynecological, and orthopedic surgeries, with varying efficacy.^{1,2,3} Studies evaluating the efficacy of liposomal bupivacaine for regional procedures have also displayed mixed results.⁴

Liposomal bupivacaine has recently been approved by the FDA for use in brachial plexus blocks for patients undergoing major shoulder surgery.⁵ Per the manufacturer's data, ISB using liposomal bupivacaine provided significant pain reduction in the first 48 hours after surgery compared to ISB using placebo, establishing that liposomal bupivacaine has an opioid sparing effect in this patient population without significant risk.

A recent study compared the addition of liposomal bupivacaine to plain bupivacaine for interscalene blocks in patients undergoing shoulder surgery, and found a modest improvement in pain.⁶

At a cost of about \$300 per administration for liposomal bupivacaine, there are significant economic impacts to be considered, given that plain bupivacaine is significantly less expensive. Data from future studies are required to perform a cost-benefit analysis for this new drug.

Common and relatively inexpensive adjuvants have been shown to extend the duration of analgesia provided by interscalene nerve blocks (ISB) using plain bupivacaine, with a significant analgesic effect extending up to 48 hours postoperatively.⁷⁻⁹

To date, there has been no study comparing the efficacy of ISB using liposomal bupivacaine vs plain bupivacaine with these common adjuvants, such as epinephrine, dexamethasone, clonidine, and buprenorphine.

The purpose of this study is to determine whether the use of plain bupivacaine with common adjuvants for ISB provides non-inferior analgesic results compared to the use of liposomal bupivacaine for ISB, in patients undergoing primary total shoulder arthroplasty.

LB= Liposomal bupivacaine

PBA= Plain bupivacaine + adjuvants

ISB= Interscalene peripheral nerve block

Single Injection interscalene brachial plexus nerve block with adjuvants vs. Liposomal bupivacaine
interscalene brachial plexus nerve block for total shoulder arthroplasty

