5.5 Safety Monitoring Plan

Any adverse safety events occurring in the perioperative period (pre-op, intra-op, or PACU) will be reported by the attending anesthesiologist to the PI and the study coordinator. The PI will record these events and contact the patient to determine the result of these events and arrange any follow-up care that is necessary.

Patients will be instructed to contact the research team to report any adverse events that occur in the postoperative period (after discharge). Patients will be given daytime and evening contact numbers for the PI and the Regional Anesthesia team (on call 24/7) via telephone. These events will be reported to the PI and the study coordinator. The PI will record these events and contact the patient to determine the result of these events and arrange any follow-up care that is necessary.

Serious adverse events will be reviewed by the PI and reported to the IRB promptly within 48 hours. Adverse events of special interest include the following: local anesthetic systemic toxicity, chest pain, shortness of breath, altered sensorium, tinnitus, visual disturbance, and severe dizziness.

6 Statistical Considerations

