7.0 Adverse Event Reporting

Adverse event means any untoward medical occurrence associated with the use of a drug in humans, whether or not considered drug related.

Life-threatening adverse event or life-threatening suspected adverse reaction. An adverse event or suspected adverse reaction is considered "life-threatening" if, in the view of either the investigator or sponsor, its occurrence places the patient or subject at immediate risk of death. It does not include an adverse event or suspected adverse reaction that, had it occurred in a more severe form, might have caused death.

Serious adverse event or serious suspected adverse reaction. An adverse event or suspected adverse reaction is considered "serious" if, in the view of either the investigator or sponsor, it results in any of the following outcomes: Death, a life-threatening adverse event, inpatient hospitalization or prolongation of existing hospitalization, a persistent or significant incapacity or substantial disruption of the ability to conduct normal life functions, or a congenital anomaly/birth defect. Important medical events that may not result in death, be life-threatening, or require hospitalization may be considered serious when, based upon appropriate medical judgment, they may jeopardize the patient or subject and may require medical or surgical intervention to prevent one of the outcomes listed in this definition. Examples of such medical events include allergic bronchospasm requiring intensive treatment in an emergency room or at home, blood dyscrasias or convulsions that do not result in inpatient hospitalization, or the development of drug dependency or drug abuse.

Suspected adverse reaction means any adverse event for which there is a reasonable possibility that the drug caused the adverse event. For the purposes of IND safety reporting, "reasonable possibility" means there is evidence to suggest a causal relationship between the drug and the adverse event. Suspected adverse reaction implies a lesser degree of certainty about causality than adverse reaction, which means any adverse event caused by a drug.

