- (C) An aggregate analysis of specific events observed in a clinical trial (such as known consequences of the underlying disease or condition under investigation or other events that commonly occur in the study population independent of drug therapy) that indicates those events occur more frequently in the drug treatment group than in a concurrent or historical control group.

In case a cardiac or neurological AE of special interest (AESI) or serious AE (SAE) occurs during the study, if the investigator considers that the event may be related to study treatment or suggests the possible occurrence of local anesthetic systemic toxicity (LAST; with or without the need for treatment [e.g., intralipids]), or if a plausible etiology for the event cannot be found, vital signs, and clinical laboratory tests will be performed per institutional standard of care of such occurrence. Cardiac AESIs include chest pain, abnormal/irregular heart rate, and shortness of breath requiring intervention.

Single Injection interscalene brachial plexus nerve block with adjuvants vs. Liposomal bupivacaine interscalene brachial plexus nerve block for total shoulder arthroplasty

Neurologic AESIs include seizure, altered mental status/ altered sensorium, tinnitus, visual disturbance, and severe dizziness.

This study involves a single administration of the study drug for the analgesic block; therefore, subjects should not be withdrawn from the ongoing study assessments as long as they are willing and able to continue with the follow-up schedule according to the protocol in order to obtain analgesic and safety data. Any subject exhibiting undesirable AESIs will receive appropriate treatment at the discretion of the investigator.

Subjects will be monitored for the occurrence of all potential adverse events by research personnel. This clinical research study will be paused after one death where a clear alternate cause is not readily apparent. The study will be paused after 2 non-fatal SAEs where a clear alternate cause is not readily apparent; the study will be paused after 3 moderate or severe adverse events of special interest. The adverse event(s) will be assessed by all investigators for causality and relationship prior to the study enrollment being resumed. Assessment of adverse event severity will be assessed and graded as per the definitions noted in Appendix I.

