Appendix H- Data Collection Form

| | |
|--------------|-----------------------------------------|
| | Assigned Study Number: |
| | WakeOne MRN |
| Demographics | Age |
| | Sex |
| Procedure | Comorbidities |
| | Pre-surgical analgesics |
| Medical Hx | Preop pain score |
| | Pre-op multimodal analgesics |
| | Post-Block assessment |
| Pre-Op | Intra-op Narcotics (PO oxy equivalents) |
| | Pain score in PACU p/t discharge |
| Intraop | PACU block assessment |
| | PACU opioids (PO oxy equivalents) |
| | +6hr worst pain score (VAS) |
| PACU | |
| | |

Single Injection interscalene brachial plexus nerve block with adjuvants vs. Liposomal bupivacaine interscalene brachial plexus nerve block for total shoulder arthroplasty

| | |
|------------------|-----------------------------------------------------------------------------------------------------------------------------------------------------------------------------------------------------------------------------------------------------------------------------------------------------------------------------------------------------------------------------------------------------------------------------------------------------------------------------------------------------------------|
| | 
+12h worst pain score (VAS)
 
+24h worst pain score (VAS)
 
+36h worst pain score (VAS)
 
+48h worst pain score (VAS)
 
+6hr opioid use (PO oxy eq)
 
+12h opioid use (PO oxy eq)
 
+24h opioid use (PO oxy eq)
 
+36h opioid use (PO oxy eq)
 
+48h opioid use (PO oxy eq)
 
Likert Satisfaction #1
 
Likert satisfaction #2 Nonopiod Analgesics Used Side effect evaluation (Itching, Nausea/vomiting)
 |
| Post OP | |
| Off study | 
("OFF" if applicable)
 
Reasons:
 |

Date of study completion:

Evaluable subject?

Protocol deviations?

Single Injection interscalene brachial plexus nerve block with adjuvants vs. Liposomal bupivacaine interscalene brachial plexus nerve block for total shoulder arthroplasty

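### No scheduled item asks whether limb sensation and strength have returned, and scheduled contact ends at 48 h, so detection of a deficit that outlasts the block rests on unprompted patient reports

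*Combined protocol and SAP*

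**What the plan says.** **Contacts.** Section 5.4 ends follow-up with assessments "then at 12, 24, 36 and 48 hours after surgery both in the hospital and at home via phone call". In Table 1 (Section 5.0) the row "Patient satisfaction assessed via Likert scale. Review of potential adverse events" is marked once, in the 48 h column. Section 4.2.3.1 places the adverse-event evaluation at the same time.

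**Expected analgesia.** Section 1.0 says that the liposomal block "provided significant pain reduction in the first 48 hours after surgery compared to ISB using placebo", and describes the adjuvant block as one "with a significant analgesic effect extending up to 48 hours postoperatively".

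**What is recorded.** Appendix H has a post-block assessment before surgery and a "PACU block assessment"; no later block item follows. The side effects named in Appendices E and H are itching and nausea or vomiting. Limb numbness or weakness is not among the events of special interest in Sections 5.5 and 7.0. It has no row of its own in Appendix I and would fall under the general clinical-event row.

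**Serious events.** The Section 7.0 definition includes "a persistent or significant incapacity or substantial disruption of the ability to conduct normal life functions". The same section states: "The study will be paused after 2 non-fatal SAEs where a clear alternate cause is not readily apparent".

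**Reporting after discharge.** Section 5.5 tells patients to report any adverse event to the research team and gives them numbers for the investigator and for a regional anesthesia team that is always on call. The investigator must then contact the patient and establish the outcome. No end date is set.

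**The concern.** At 48 h, numbness or weakness may be either the tail of the block or an injury. Telling them apart needs two things: a question about whether function has returned, and a later contact for those in whom it has not. The plan schedules neither. A patient with a lasting deficit enters the safety data only by recognising it as abnormal and calling, or by mentioning it unprompted at 48 h.

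Slow block resolution and lasting nerve deficit are harms on which a long-acting formulation and a four-adjuvant mixture could plausibly differ. If such events are under-reported, the pause rule becomes less sensitive to one kind of event it covers. A count of zero at the end could also not be told apart from non-reporting. The interim look in Section 6.6, meant to detect severe side effects, draws on the same safety data.

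**Working it through.** The plan gives no figure on this point, so there is none to reproduce. The check is a comparison of sections, followed by an illustration.

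**1. Sections side by side**

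- Last scheduled contact: 48 h (Section 5.4, Table 1).
- Scheduled adverse-event reviews: one, at 48 h (Table 1).
- Analgesic period described: first 48 h for the liposomal block, up to 48 h for the adjuvant block (Section 1.0).
- Last block assessment: PACU (Appendix H).
- Patients with a planned item on block resolution after PACU: 0 of 80 (Appendices C, E and H; sample size from Section 6.3).
- Route for a deficit that persists after 48 h: patient-initiated report, then investigator follow-up (Section 5.5).
- Consequence if it is classed as serious without a clear alternate cause: counts towards the two-event pause (Section 7.0).

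The route exists and leads to the pause rule. What is missing is any prompt to use it.

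**2. How much the pause rule depends on reporting (illustration)**

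Inputs: n = 80 (Section 6.3). Assumed: p, the true rate of persistent deficit, and s, the share that becomes known to the team; the documents give neither. Patients are taken as independent, and every known case as a serious event without a clear alternate cause.

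With q = p × s, P(at least 2 known) = 1 − (1 − q)^80 − 80 q (1 − q)^79.

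Example, p = 2% and s = 1: 1 − 0.98^80 − 1.6 × 0.98^79 = 1 − 0.199 − 0.324 = 0.477.

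| Assumed p | s = 1 | s = 0.5 | s = 0.25 | s = 0 |
|---|---|---|---|---|
| 1% | 0.19 | 0.06 | 0.02 | 0 |
| 2% | 0.48 | 0.19 | 0.06 | 0 |
| 5% | 0.91 | 0.60 | 0.26 | 0 |

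The chance is zero only if no deficit is ever reported.

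**3. What a count of zero would mean**

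The one-sided 95% upper limit with 0 of 80 known is 1 − 0.05^(1/80) = 3.7% for the rate of known deficits. The corresponding true rate is that limit divided by s: 3.7% if all become known, 0.0368 / 0.5 = 7.4% if half, and 0.0368 / 0.25 = 14.7% if a quarter. The plan has no means of saying which applies.

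**The case against.** A reader might infer that a lasting deficit cannot be recognised at all, or that the pause rule depends on events the trial cannot see. The documents do not support this. Section 5.5 asks for reports of any adverse event after discharge, supplies contact numbers, obliges the investigator to follow up, and sets no end date. A deficit reported on day 5 can be classed as serious and counted. The pause rule also covers deaths, other unexplained serious events and events of special interest.

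A reader might also subtract 48 h of follow-up from 48 h of drug action and conclude that there are 0 hours of observation after the block. Section 1.0 does not give the figures for that. It describes pain relief, not the duration of sensory, motor or phrenic block, and for the adjuvant block 48 h is an upper limit.

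Three further points stand:

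- Breathing is partly covered, because shortness of breath is an event of special interest (Section 7.0 adds that it must require intervention) with its own pause trigger.
- Section 7.0 says research personnel monitor for all potential adverse events, and the Off-Study Form refers to a case report form for adverse events, so Appendix H may not be the only record.
- The objectives concern pain and opioid use, and no comparison of persistent deficits is planned.

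Nothing in the documents says what patients are told to expect about numbness or weakness. The consent pages were removed before review, and their absence is not held against the plan.

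These points remove the claim that detection is impossible. They do not supply a question about recovery or a scheduled contact at which to ask it.

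**Conclusion.** The concern holds as a gap in ascertainment. Scheduled contact and the only scheduled adverse-event review end at 48 h, and no planned item at any time after PACU asks whether limb sensation and strength have returned. Detection of a deficit outlasting the block therefore rests on unprompted reports and is likely to be incomplete, although such a deficit may meet a serious-event criterion that feeds the pause rule.

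The firm size is 0 of 80 patients with a planned block-resolution item after PACU. That describes the planned items; it does not mean that 0 of 80 deficits would be found. The loss of sensitivity is conditional: at an assumed 2% rate, the chance of two known cases falls from 0.48 to 0.19 if half are reported. Both the rate and the reporting share are assumptions. The primary outcome and its analysis are unaffected.

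**What to change.** - At the existing 48 h call, add one yes/no item: are limb sensation, strength and breathing back to the pre-operative state? Record it in Appendix H. Because Section 3.2.3 excludes pre-existing neurological dysfunction of the operative limb, the limb part of the answer has a clear baseline.
- Re-contact every patient who answers no until the outcome is known, and code it with the outcome categories already in Section 7.0.
- Where a routine surgical follow-up visit takes place, review its chart note for persisting deficits and serious events, and count any serious event found towards the pause rule. The documents do not describe such a visit, so this part rests on an assumption.
- Keep the patient-initiated reporting of Section 5.5 open. Do not make the surgical visit the end of serious-event collection, since that would cut off a route that now has no end date.

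The cost is one question per patient, a few extra calls (the number depends on how many answer no), up to 80 chart look-ups and a slightly later close of the safety data. No new visit or procedure is needed.
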